9.2.3.4 Serious Adverse Events

Information on SAEs will be collected and assessed throughout the trial, from inclusion until 6 months after the last vaccination.

Any SAE occurring at any time during the trial will be reported by the Investigator through the EDC system and according to the completion guidelines provided by the Sponsor. All information concerning the SAE is to be reported (including, but not limited to, start and stop dates, diagnosis, seriousness), either as part of the initial reporting or during follow-up reporting if relevant information became available later (e.g., outcome, medical history, results of investigations, copy of hospitalization reports). The Investigator will assess the causal relationship of the SAE with the investigational product as either “Not related” or “Related”, as described in previous section and specifically, in [Section 10.4](#).

See [Section 10](#) for further details on SAE reporting.

9.2.3.5 Adverse Events of Special Interest

The following AESIs will be assessed during the overall conduct of the trial:

^a ICH Guidelines, Clinical Safety Data Management E2A

- anaphylactic reactions
- encephalitis
- convulsions

These AESIs are considered by the Sponsor to be relevant for the monitoring of the safety profile of investigational products. They will be collected during the entire participation of a subject in the trial and are to be reported as SAEs according to the procedure described in [Section 10](#).

These AESIs have been defined based on existing post-marketing safety data (important identified or potential risks) of other rabies vaccines. For each AESI, the standard case definitions from the Brighton Collaboration will be used([23](#)) ([24](#)) ([25](#)).

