In addition, the following AEs have been reported during the post-marketing surveillance of the Verorab vaccine. Because these events are reported voluntarily from a population of uncertain size, it is not always possible to reliably estimate the frequency or establish a causal relationship of exposure to Verorab:

- Immune system disorders: anaphylactic reactions, serum sickness type reactions
- Nervous system disorders: encephalitis, convulsions, sudden sensorineural hearing loss
- Gastrointestinal disorders: vomiting

Serious hypersensitivity reactions may occur after any vaccination, and they are considered Important identified risks with Verorab. Other serious events listed above (encephalitis, convulsion, sudden sensorineural hearing loss), are considered Important potential risks, because although cases have been reported from post-marketing experience with Verorab, their causal association with the vaccine have not been established.

All identified and potential risks of Verorab are considered as potential risks for VRVg, even though they have not been observed with VRVg specifically to date.

It is to note that the prefilled diluent syringe tip caps used for both VRVg-1 and VRVg-2 may contain natural rubber latex which may cause allergic reactions in latex sensitive individuals.

Imovax Rabies

The following risks have been identified with the use of Imovax Rabies as currently reported in the Company Core Data Sheet:

- Very common (>10%): adenopathy, headache, nausea, myalgia, injection site pain, erythema, and induration (swelling/hardness), hematoma, malaise
- Common (>1% and <10%): Allergic reactions with skin disorders such as urticaria and rash, or respiratory manifestations such as dyspnea and wheezing, dizziness, abdominal pain, vomiting, diarrhea, arthralgia, injection site pruritus (itching), fever, chills (shivering)

In addition, the following AEs have been reported very rarely (<1/100000) during the post-marketing surveillance of Imovax Rabies. Based on spontaneous reporting, their frequencies have been estimated using the number of reports and the estimated number of patients. However, the exact incidences cannot be precisely calculated.

- Immune system disorders
- Skin allergic reactions pruritus (itching), edema.
 - Anaphylactic reactions
 - Serum sickness type reactions

These reactions have been associated with the presence of betapropiolactone-altered human albumin in Imovax Rabies.

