- 10) Remind the subject to notify the site in case of an SAE or pregnancy (for woman of childbearing potential).
- 11) Complete the relevant source document information and CRF pages for this visit.

V06 (14 [± 3] days after VAC5): Collection of Safety Information and Blood Sample

- 1) Review the DC3 with the subject, including any adverse events, medications, or therapy that occurred since vaccination by Investigator or delegate. The subject will continue using the DC1 to collect safety information until the next visit.
- 2) Conduct a physical examination.

- 3) Obtain the fourth 5mL blood sample (see [Section 7.1](#) for detailed instructions regarding the handling of blood samples).
- 4) Remind the subject to notify the site in case of an SAE or pregnancy (for woman of childbearing potential).
- 5) Complete the relevant source document information and CRF pages for this visit.

V07 (28 [± 3] days after VAC5): Collection of Safety Information

- 1) Review and collect the DC3 with the subject, including any adverse events, medications, or therapy that occurred since vaccination by Investigator or delegate.
- 2) Conduct a physical examination.
- 3) Give the subject with the memory aid (MA) to record any SAEs or AESIs that may occur during the 6-month safety follow-up.
- 4) Remind the subject to notify the site in case of an SAE or pregnancy (for woman of childbearing potential).
- 5) Complete the relevant source document information and CRF pages for this visit.

V08 (6 months [± 14] days] after VAC5): Collection of Safety Information and Blood Sample

- 1) Review MA by Investigator or delegate.
- 2) Obtain the fifth 5 mL blood sample (see [Section 7.1](#) for detailed instructions regarding the handling of blood samples).
- 3) Complete the relevant source document information, complete the termination record of the CRF, and enter the subject's termination information in the IVRS / IWRS.

SAEs and AEs That Are Related to Vaccination or That Led to Discontinuation:

At any time during the study, a subject who experiences an SAE or an AE must be followed if *either* of the following is true:

- The SAE or AE is considered by the Investigator to be related to vaccination, and is not resolved by the end of the subject's participation in the trial
- The subject has been discontinued from the trial because of the SAE or AE

Any such subject must be followed until the condition resolves, becomes stable, or becomes chronic.

Pregnancy cases*

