Unsolicited AE / AR:

An unsolicited AE is an observed AE that does not fulfill the conditions prelisted in the CRF in terms of diagnosis and / or onset post-vaccination, i.e., excluding solicited reactions, e.g., if headache between D0 and D7 is a solicited reaction (i.e., prelisted in the CRF), then a headache starting on D7 is a solicited reaction, whereas headache starting on D8 post-vaccination is an unsolicited AE.

An unsolicited non-serious AE is an unsolicited AE excluding SAEs.

Injection Site Reaction:

An injection site reaction^a is an AR at and around the injection site. Injection site reactions are commonly inflammatory reactions.

Systemic AE:

Systemic AEs are all AEs that are not injection site reactions. They therefore include systemic manifestations such as headache, fever, as well as localized or topical manifestations that are not associated with the vaccination site, e.g., erythema that is localized but that is not at the injection site.

In addition, reactions reported at the site(s) of HRIGs administration will be reported as systemic AEs.

^a All injection site AEs are considered to be related to vaccination and are therefore all *injection site reactions*.

Adverse Events of Special Interest (AESIs):

AEs of special interest are AEs that are considered by the Sponsor to be relevant for the monitoring of the safety profile of the investigational vaccine. The following AESIs are defined: anaphylactic reactions, encephalitis and convulsions.

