12.1.2.2 Statistical Methods

The safety analysis will report the occurrence of solicited reactions and the incidence of unsolicited AEs, including SAEs and AESIs, over the safety observation period by vaccine group. Injection site reactions will be collected up to 7 days after each injection, systemic AEs will be collected between each vaccination and up to 28 days after the last injection. The following AEs will be considered as AESIs: anaphylactic reactions, encephalitis and convulsions. In order to

avoid any under-estimation of the incidences, the number of subjects with documented safety will be used as denominator of the frequencies.

For safety parameters, 95% CIs of point estimates of proportion will be calculated using the exact binomial distribution (Clopper-Pearson method) for proportions (26) .

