4.3 Derived Endpoints: Calculation Methods

4.3.1 Safety

Terms used in the standard safety tables to describe the safety events are specified below.

- AE: Adverse event includes immediate, solicited, and unsolicited non-serious, or serious event
- AR: Adverse reaction corresponds to related AE
- Immediate: Unsolicited systemic non-serious AE ticked “immediate (within 30 minutes from the vaccination)” by the investigator in the electronic case report form (eCRF) or SAE with time of onset within 30 minutes
- Solicited reaction: Event pre-listed in the eCRF, and which occurred during the solicited period
- Unsolicited AE: AE recorded in the eCRF as unsolicited or SAE forms, excluding solicited reaction. Therefore, include immediate AE.

Unsolicited non-serious injection site reactions are always recorded without relationship and analyzed as ARs.

Unsolicited AEs analyzed are AEs up to 28 days +3 days after vaccination. Unsolicited AEs occurring after the defined period - and which are not SAEs - will be presented in a separate listing.

- SAE: Unsolicited AE considered serious by the investigator (reconciled with Global Pharmacovigilance database)
- Adverse event of specific interest (AESI): the list of Medical Dictionary for Regulatory Activities (MedDRA) preferred terms (PT) defined in the protocol to select these AEs in the database:
 - Anaphylactic reaction (PT)
 - Encephalitis (PT)

- Convulsion (PT)

4.3.1.1 **Solicited Reactions**

4.3.1.1.1 **Daily Intensity**

All daily records for solicited reactions will be derived into daily intensity according to the following classification: None, Grade 1, Grade 2, Grade 3, or Missing.

For the derivation of daily intensities the following sequential steps will be applied:

1) For solicited reactions (except for fever) with an Investigator presence recorded as "No" and with all daily records missing, all daily intensities will be derived as "None."

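### Sudden sensorineural hearing loss is ranked as an important potential risk but is on no AESI list, so a case judged non-serious has no assured collection after D56

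*Protocol*

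**What the plan says.** **Risk ranking (protocol 1.3.2).** From Verorab post-marketing data the protocol states: "Serious hypersensitivity reactions may occur after any vaccination, and they are considered Important identified risks with Verorab". It continues: "Other serious events listed above (encephalitis, convulsion, sudden sensorineural hearing loss), are considered Important potential risks". It then extends these to the trial vaccine: "All identified and potential risks of Verorab are considered as potential risks for VRVg". It adds that they have not been seen with VRVg so far and that a causal link for the three potential risks is not established.

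**Basis of the AESI list (protocol 9.2.3.5).** "These AESIs have been defined based on existing post-marketing safety data (important identified or potential risks) of other rabies vaccines".

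**The lists.** Protocol 9.2.1: "The following AESIs are defined: anaphylactic reactions, encephalitis and convulsions". Protocol 12.1.2.2: "The following AEs will be considered as AESIs: anaphylactic reactions, encephalitis and convulsions". Protocol 9.2.3.5 gives the same three. SAP 4.3.1 introduces "Adverse event of specific interest (AESI): the list of Medical Dictionary for Regulatory Activities (MedDRA) preferred terms (PT) defined in the protocol" and names one preferred term for each of the three.

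**What AESI status brings.** Under protocol 9.2.3.5 an AESI is collected for the subject's whole participation and goes through the SAE reporting procedure, which under 10.1 means 24 hours. Other non-serious unsolicited systemic events are collected up to 28 days after the fifth dose (protocol 9.2.2). At V07 the site hands out the memory aid "to record any SAEs or AESIs that may occur during the 6-month safety follow-up" (protocol 5.1.4); sections 5.1.1 and 5.1.3 describe the same scope.

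**The concern.** The protocol puts hearing loss in the same parenthesis as encephalitis and convulsion. It then gives those two a special collection and reporting route and gives hearing loss none, without comment.

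Two things are at stake:

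- **Capture.** After D56 the only adverse events that subjects are clearly asked about are SAEs and AESIs. Hearing loss that the investigator does not judge serious is neither.
- **Meaning of the AESI table.** A reader who knows the stated basis of the list would take an empty AESI table to cover the risks ranked as important. It would cover three of the four.

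The trial has no independent data monitoring committee (protocol section 3), and it selects the VRVg-2 dosage to take into Phase III. That is a reason to have named risks collected in full.

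**Working it through.** The plan gives no figure on this point to reproduce. The check compares the sections and works out the length of the window.

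**1. Risk list against AESI list**

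| Risk ranked as important in protocol 1.3.2 | Rank | Represented among the AESIs |
|---|---|---|
| Serious hypersensitivity | identified | yes, as anaphylactic reactions |
| Encephalitis | potential | yes |
| Convulsion | potential | yes |
| Sudden sensorineural hearing loss | potential | no |

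Three of four are represented. The same three appear in protocol 9.2.1, 9.2.3.5 and 12.1.2.2 and in SAP 4.3.1, so this is not a slip in one section.

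**2. Route for a hearing-loss case**

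| Onset | Judged serious | Judged non-serious |
|---|---|---|
| Up to D56 | SAE; reported within 24 hours | Unsolicited event; tabulated by preferred term, not expedited, not in the AESI summary |
| D56 to M7 | SAE; reported within 24 hours | No assured active collection |

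Only the lower right cell is a collection gap. The upper right cell differs from an AESI in reporting and tabulation, not in capture.

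**3. Length of the window**

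Inputs: VAC5 at D28, V07 at D56 and V08 at 6 months after VAC5 (table of study procedures). Assumption: 6 months is 180 to 183 days. Visit windows are ignored.

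- Lower: 28 + 180 = D208; 208 − 56 = 152 days; 152/208 = 73%.
- Upper: 28 + 183 = D211; 211 − 56 = 155 days; 155/211 = 73%.

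This applies to all 320 subjects, of whom 3 × 80 + 40 = 280 are assigned to VRVg and 3 × 80 = 240 to VRVg-2.

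**4. What full capture could show**

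With zero cases in n subjects, the exact two-sided 95% upper limit is 1 − 0.025^(1/n). For n = 280 it is 1.31%; for n = 240 it is 1.53%. Even with complete collection the trial could not measure a rare rate. The benefit lies in not missing an individual case.

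**The case against.** **The list need not contain every ranked risk.** Protocol 9.2.3.5 says the AESIs were based on such risks, not that each one becomes an AESI, and 9.2.1 describes them as events the sponsor considers relevant. A reader might infer that the list contradicts its own basis. The text does not go that far. A possible rationale is that the three chosen events are also reported for Imovax Rabies in 1.3.2, whereas hearing loss appears only under Verorab. The protocol does not state this, and 1.3.2 gives the important-risk ranking only for Verorab. What stands: this is an unexplained omission, not a proven error.

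**A serious case is covered.** Protocol 1.3.2 itself groups hearing loss with serious events. A case with significant disability, or judged an important medical event, is an SAE under 9.2.1 and is collected to M7 under 9.2.3.4. So it would be wrong to infer that hearing loss is followed only to D56. What remains is dependence on the investigator's judgement. The examples of important medical events in 9.2.1 mention convulsions without hospitalization but not hearing loss.

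**A non-serious late case might still surface.** The synopsis and protocol 11.1 describe the memory aid more loosely, as a record of safety information or events. SAP 4.3.1 and 5.1.2.2.1 list late non-serious events separately. A volunteered case could therefore reach a listing, but none of this makes anyone ask for it.

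**Calendar time is not risk.** A reader might take 73% of follow-up as 73% of the risk. The documents give no onset window for hearing loss, and all five doses plus 28 days after the last are covered by unsolicited-event collection. The objection stands in full.

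**Adding a term may have side effects.** AESIs go through the SAE route. A related SAE is a definitive contraindication under protocol 5.2.7.2 and, during recruitment, suspends enrollment and vaccination under 5.5. The protocol does not say whether an AESI that meets no seriousness criterion counts for those rules. This also stands, and the question already exists for the three present AESIs.

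**Conclusion.** The point holds in a narrow form. Hearing loss is one of four risks ranked as important in protocol 1.3.2 and the only one not represented on any AESI list, with no reason given. The collection gap is limited to cases that start after D56 and are judged non-serious, over about 152 to 155 days per subject. Before D56 the difference is only in expedited reporting and AESI tabulation.

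This rests on 6 months being 180 to 183 days, and on the memory aid following the narrower scope in protocol 5.1.1, 5.1.3 and 5.1.4; the form itself is not among the documents. Few or no cases are expected. The change is worth making because it is cheap and makes the AESI table match its stated basis, not because any planned estimate would move.

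**What to change.** - Add sudden sensorineural hearing loss to the AESI lists in protocol 9.2.1, 9.2.3.5 and 12.1.2.2, and to the memory-aid prompt.
- Add the corresponding preferred term to SAP 4.3.1, so that the AESI summaries in SAP 5.1.2.2.1 include it.
- Give a working case definition based on the reported diagnosis, with no added hearing test. The definitions cited in protocol 9.2.3.5 cover only the present three events.
- State whether an AESI reported by the SAE route but meeting no seriousness criterion counts as an SAE for protocol 5.2.7.2 and 5.5, so that these sections and 9.2.3.5 are reconciled. The choice is the sponsor's.

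A sentence explaining why hearing loss was left out would settle the wording but leave the collection gap.

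The cost is one term in existing text, a short case definition and possibly one or two extra expedited reports. No visit, procedure or sample-size change is needed.

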9.3 Efficacy

No clinical efficacy data will be obtained in the trial.

10 Reporting of Serious Adverse Events

In order to comply with current regulations on SAE reporting to health authorities, the Investigator must document all SAEs regardless of causal relationship, and notify the Sponsor and the Clinical Research Associate (CRA) within the notification timelines stated in the following sections. The Investigator will give access and provide the Sponsor and the CRA with all necessary information to allow the Sponsor to conduct a detailed analysis of the safety of the investigational products. It is the responsibility of the Investigator to request all necessary documentation (e.g., medical records, discharge summary, autopsy) in order to provide comprehensive safety information. All relevant information (including diagnosis, symptoms and their evolution, relevant personal and family medical history, concomitant treatments at the time of SAE onset, details of etiological investigations including all clinical and laboratory results, etc...) must then be transcribed into the eSAE Form.

10.1 Initial Reporting by the Investigator

SAEs occurring during a subject's participation in the trial or experiment must be reported within 24 hours to the Sponsor's GPE Department and to the CRA. Every SAE must be reported, even if the Investigator considers that it is not related to the vaccine. The SAE form must be signed by a licensed physician (M.D. or D.O.) for whom the task is listed on the Study Task Delegation and Signature List after each update to the Form.

The Investigator must complete the “eSAE Form” in the EDC application. After validation, an e-mail alert will automatically be sent to the GPE mailbox, the CRA and the Clinical Team Leader (CTL). This message will include the country, the study code, the subject number, whether the report is initial or a follow-up, the diagnosis and / or symptoms, the seriousness criteria, the relationship, if related, and the outcome, if fatal.

If the EDC system is unavailable, the site must notify the Sponsor using the paper version of the SAE Reporting Form, as follows:

The Investigator must complete the SAE Reporting Form, check off the “Initial Reporting Form” box, and send it to the Sponsor by one of the following means:

- By fax, to the following number: [name]
- In PDF format to the following e-mail address, using a method of transmission that includes password protection: [contact]

When the system becomes available, the Investigator must transcribe the information from the paper version of the eSAE Form into the EDC system.

If there is need for urgent consultation, the Investigator is to contact a designated Sponsor representative. The contact information is provided in the “List of Investigators and Centers Involved in the Trial” document.

10.2 Follow-up Reporting by the Investigator

The eSAE Form completed initially must be updated within 24 hours after the Investigator has become aware of any new relevant information concerning the SAE (e.g., outcome, precise description of medical history, results of the investigation). After validation, an e-mail alert will be sent automatically to the GPE Department and to the CRA. All relevant information must be included directly in the eSAE Form. Copies of documents (e.g., medical records, discharge summary, autopsy) may be requested by the GPE Department.

The anonymity of the subject must always be respected when forwarding this information.

10.3 Reporting of SAEs Occurring After a Subject Has Completed the Study

Any SAE that occurs after a subject has completed the study but that is likely to be related to the product or to the experiment must also be reported as soon as possible. In such a case, the reporting procedure to be followed is identical to that described in [Section 10.1](#).

10.4 Assessment of Causality

The causal relationship between the SAE and the product will first be evaluated by the Investigator, using the following definitions:

0 - Not related: The AE is clearly / most probably caused by other etiologies such as an underlying condition, therapeutic intervention, or concomitant therapy; or the delay between vaccination and the onset of the SAE is incompatible with a causal relationship; or the SAE started before the first vaccination.

1 - Related: There is a “reasonable possibility” that the SAE was caused by the vaccination, meaning that there is evidence or arguments to suggest a causal relationship.

(ICH Guidelines, Clinical Safety Data Management E2A)

Following this, the Sponsor’s Global Safety Officer (GSO) will also assess the causal relationship to the product, based on the available information and current medical knowledge.

The decision to modify or discontinue the trial may be made after mutual agreement between the Sponsor and the Investigators.

